7.3.2 Intensification of pharmacotherapy

Proportion of patients with intensification of pharmacotherapy from baseline to end of study will be compared between the Immediate Results and Delayed Results arm using either a Z-test of proportions or chi-squared test. In the event of small cell counts, we will employ Fisher's exact test to ensure the validity of the results. We will compute the relative risk and 95% confidence intervals to quantify the strength and direction of the association. Potential confounders may be adjusted for by using logistic regression. Frequencies and proportions of the intensification of medications among participants will be reported by randomization arm. Exploratory analyses may compare participant medication trajectories between groups, including intensification, unchanged prescription status, or deintensification status at baseline, 3 months, and 6 months using a generalized linear model fit with generalized estimating equations.²⁶

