4.5 Baseline patient characteristics

Baseline characteristics will be summarized and presented for participants in the ITT populations. Standard statistical summaries, depending on data type and distribution, will be presented as 1) total numbers of participants with each characteristic (n) and as a proportion (%) of each group stratified by randomization arm or 2) as means and standard deviations (if normally distributed) or medians and interquartile ranges (IQR) (if non normally distributed) stratified by randomization arm. No statistical testing will be carried out for participant baseline characteristics or measures between treatment groups.

At minimum, the below participant baseline characteristics, including the pre-specified baseline measurements of the study outcomes described in Section 6.0, will be derived and reported:

| Baseline characteristic | How derived | Presentation |
|---|---|----------------------------------|
| Age in years | As calculated using EHR administrative data relative to date of consent and enrollment. | mean (SD) / median (IQR) |
| Gender / Sex | As determined by EHR administrative data. | n (%) |
| Race | As determined by EHR administrative data and/or data collected from baseline survey. | n (%) |
| Ethnicity | As determined by EHR administrative data and/or data collected from baseline survey. | n (%) |
| Socioeconomic Status / Area Deprivation Index | Calculated using income, geographic, and other EHR administrative data.(ADI) ⁹ | n (%) |
| Self-reported health status and quality of life | As determined by data collected from baseline survey. (VR-12) ¹⁰⁻¹² | mean (SD) / median (IQR) |
| Self-reported patient activation | As determined by data collected from baseline survey. (PAM-13) ¹³ | mean (SD) / median (IQR) / n (%) |
| Beliefs about medications | As determined by data collected from baseline survey. (Beliefs About Medicines Questionnaire) ¹⁴ | mean (SD) / median (IQR) |
| Low-density lipoprotein cholesterol | As determined by EHR data. | mean (SD) / median (IQR) |
| Lipid-lowering pharmacotherapy | As determined by data collected from baseline survey and EHR data. | n (%) |

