7.0 Analysis methods

7.1 Covariate adjustment

No prespecified covariate adjustment is planned. If any covariate adjustment is deemed necessary during analysis or used to improve the precision of estimates, rationale and methods will be fully described in the final manuscript(s).

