7.4.6 Continuous outcome measures

The following continuous measures are compared between treatment groups among the ITT populations using standard linear methods:^{29,30}

- Self-reported patient activation (linear score)
- Self-reported beliefs about medications
- Self-reported feelings about genomic testing results (Immediate Results arm only, score)

Mean and standard deviation (or median and IQR, if applicable) of continuous scores associated with end-of-study self-reported responses to study surveys will be reported by treatment group. Analysis of covariance (ANCOVA) is used to compare continuous follow-up measures, including participant baseline measures, when available, and treatment group assignment. Treatment effect is characterized by treatment versus control arm, presented as mean follow-up estimates with accompanying standard errors, 95% confidence intervals and *P* values. In the presence of substantial missing data, mixed modeling or other repeated measures designs may be implemented.

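### Intensification of pharmacotherapy: the prespecified test is valid but unadjusted, and naming two baseline covariates already collected would buy precision of uncertain, probably modest size at little cost

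*SAP*

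**What the plan says.** For this secondary outcome, section 7.3.2 says: "Proportion of patients with intensification of pharmacotherapy from baseline to end of study will be compared between the Immediate Results and Delayed Results arm". The test is a Z or chi-squared test on the raw proportions, with Fisher's exact test for small cells. The effect measure follows: "We will compute the relative risk and 95% confidence intervals to quantify the strength and direction of the association".

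Adjustment appears in three places, none of them binding:

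- Section 7.3.2: "Potential confounders may be adjusted for by using logistic regression". No covariates are named.
- Section 7.1: "No prespecified covariate adjustment is planned". It then leaves the door open: "If any covariate adjustment is deemed necessary during analysis or used to improve the precision of estimates, rationale and methods will be fully described".
- Section 7.5 ranks added covariates, for secondary outcomes as for others, as supplementary to what was prespecified.

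The two obvious covariates are in hand. Baseline LDL-C is defined in section 6.1 and listed in section 4.5. Baseline lipid-lowering pharmacotherapy is also listed in section 4.5, with its source given as "As determined by data collected from baseline survey and EHR data". Section 6.2.2 needs that regimen to score the outcome, because a new drug, a dose increase or an add-on counts only relative to baseline therapy.

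**The concern.** Which routes to intensification are open to a participant depends on the starting regimen, and the reason to intensify depends on the starting LDL-C. Both should therefore explain part of the variation in the outcome within each arm. A raw comparison of proportions leaves that variation in the error term.

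The plan frames adjustment mainly as confounder control. Randomization already deals with confounding in expectation, so the useful purpose here is precision. Section 7.1 mentions precision, but only as a choice to be made during analysis.

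At stake are the width of the interval and the power for one of two named secondary outcomes. Section 5.4 applies a Bonferroni correction to secondary outcomes, which means 0.025 each if the family is the two outcomes of section 6.2. Two lesser points follow from leaving the model open. The covariates of any adjusted analysis could be chosen after the data are seen. A plain logistic model would also give a conditional odds ratio, which does not correspond to the planned relative risk.

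**Working it through.** **1. The plan's own binary sizing.** Section 3.2 sizes the LDL-C target outcome, not intensification. For 40% versus 60%, two-sided 0.05 and 80% power, with pooled variance under the null and no continuity correction:

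n per arm = [1.960 × √(2 × 0.5 × 0.5) + 0.842 × √(0.4 × 0.6 + 0.6 × 0.4)]² / 0.20² = 96.9, so 97 per arm and 194 in total, as stated. With 20% loss, 97 / 0.8 = 121.25, so 122 per arm and 244 in total, as stated.

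**2. Inputs for intensification.** The SAP gives no rates, so these are assumptions.

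- Immediate arm 50%. This is suggested by the section 3.2 allowance for no escalation in up to half of that arm.
- Delayed arm 30%. Assumed.
- 97 per arm, borrowed from the LDL-C target calculation; 122 per arm if nearly everyone can be scored.
- One binary baseline stratum, split 50/50. Assumed.

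**3. Raw power.** The sum of the two binomial variances is 0.50 × 0.50 + 0.30 × 0.70 = 0.46. At 97 per arm, SE = √(0.46 / 97) = 0.0689, and 0.20 / 0.0689 = 2.904.

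- Alpha 0.05: Φ(2.904 − 1.960) = 83%.
- Alpha 0.025: Φ(2.904 − 2.241) = 75%.

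**4. Variance removed by the stratum.** Replace each arm's variance by the average of its two within-stratum variances.

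| Association | Immediate, two strata | Delayed, two strata | Summed within-stratum variance | Cut from 0.46 |
|---|---|---|---|---|
| Weak | 58% / 42% | 36% / 24% | 0.2436 + 0.2064 = 0.4500 | 2% |
| Moderate | 65% / 35% | 42% / 18% | 0.2275 + 0.1956 = 0.4231 | 8% |
| Strong | 75% / 25% | 50% / 10% | 0.1875 + 0.1700 = 0.3575 | 22% |

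**5. Power after adjustment**, from Φ(0.20 / √(V/n) − z), where V is the summed variance from step 4:

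| | 97 per arm, 0.05 | 97 per arm, 0.025 | 122 per arm, 0.05 | 122 per arm, 0.025 |
|---|---|---|---|---|
| Raw | 83% | 75% | 90% | 85% |
| Weak | 84% | 76% | 91% | 85% |
| Moderate | 86% | 78% | 92% | 88% |
| Strong | 91% | 85% | 96% | 93% |

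A simulation of 20,000 runs at 97 per arm, comparing the pooled Z test with a stratified Mantel-Haenszel test, gave gains of 1, 3 and 8 points at 0.05 and 1, 4 and 11 points at 0.025. The half-width of the 95% interval for the risk difference (1.96 × SE, 97 per arm) goes from 13.5 points raw to 13.3, 12.9 and 11.9.

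**6. Other assumptions.**

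- *Other rates.* At 40% versus 60% and 97 per arm, raw power is 80% at 0.05. It becomes 82%, 84%, 88% and 92% if baseline explains 5%, 10%, 20% and 30% of the variance.
- *Fewer intensified in the Delayed arm.* At 50% versus 20%, SE = √((0.25 + 0.16) / 97) = 0.065, and Φ(0.30 / 0.065 − 1.960) exceeds 99%. Adjustment then narrows the interval but adds almost no power.
- *Uneven stratum.* With the moderate gaps (30 and 24 points) and an 80/20 split, the cut is 0.8 × 0.2 × (0.30² + 0.24²) / 0.46 = 5% instead of 8%.
- *Covariates that do not predict.* A simulated logistic model standardised to a risk difference had a variance ratio of 1.01 against the raw comparison, a negligible loss.
- *Error rate under no effect* (20% in both arms, 3,000 runs). Rejection was 5.4% raw and 6.0% adjusted with a robust standard error. The Monte Carlo error is √(0.05 × 0.95 / 3,000) = 0.4 points, so the choice of interval method deserves a small-sample check.

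**The case against.** The strongest objection is that nothing here is an error. A two-proportion test with a relative risk is transparent and legitimate, and section 7.1 says openly that this is the general rule. That stands, and it sets the weight of the point.

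Four stronger readings are tempting, and the document does not support them.

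- **That the plan has no adjustment, or excludes it.** Section 7.3.2 permits logistic regression and section 7.1 names precision as a possible reason. What is missing is a prespecified role and named covariates.
- **That post hoc covariate choice could displace the main result.** Section 7.5 makes added covariates supplemental, so the unadjusted relative risk stays the prespecified result. The mismatch between odds ratio and relative risk touches only that supplement.
- **That the plan contradicts itself because it adjusts lower-ranked outcomes.** Section 7.4.6 says "Analysis of covariance (ANCOVA) is used to compare continuous follow-up measures, including participant baseline measures, when available, and treatment group assignment", and section 7.4.5 is similar. Those analyses adjust a follow-up measure for its own baseline value. Intensification has no such value, being already defined against baseline therapy. The nearer comparators, in sections 7.3.1 and 7.4.1, use the same unadjusted tests.
- **That the gain is large.** A conventional correlation of 0.5 would cut variance by 25% and lift power to 92% at 0.05 and 87% at 0.025. The SAP gives no basis for that value, and it exceeds even the strong case above.

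Two further objections reduce the size. Intensification can draw on prescription data and record review (sections 4.3.2 and 6.2.2), so fewer participants may be lost than for LDL-C. The 50/50 split is also unsupported: section 6.2.1 sets the lower target for anyone with a listed risk factor, so the share already at target may be well under half.

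The change is not wholly free either, since it needs a rule for missing or late baseline values. None of this removes the point, because the covariates are in hand and the cost is small.

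**Conclusion.** The point holds as an efficiency matter. The prespecified comparison of intensification ignores two plausibly prognostic baseline variables that the trial already collects, and the permitted adjustment is supplemental and unspecified. A reader should not infer bias or an invalid test; neither is present.

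The size cannot be established from the SAP. Under 50% versus 30% and 97 per arm, the gain is about 1 to 8 points of power at alpha 0.05 and 1 to 11 at 0.025. The weak and moderate cases, at 1 to 4 points, need the least to be assumed. At 122 per arm the moderate case adds about 2 points at 0.05 and 3 at 0.025. If the covariates turn out not to predict the outcome, the loss is negligible. This is a cheap improvement, worth making before the data are analysed.

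**What to change.** In sections 7.1 and 7.3.2:

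1. Make the main comparison of intensification a logistic model with arm, continuous baseline LDL-C and baseline lipid-lowering regimen category (for example none, statin alone, combination).
2. Use pre-randomization covariate values only. Section 4.3.1 anticipates some baseline measurements taken after randomization; treat these as missing for this model.
3. Fill missing covariate values by a simple rule that ignores arm, such as the overall mean with a missing indicator. State that this rule is exempt from the within-arm imputation of section 5.5.
4. Report the standardised (marginal) relative risk and risk difference with 95% confidence intervals, so the result stays on the scale that section 7.3.2 already uses. Name the interval method (delta method or bootstrap) and check its coverage at the expected sample size.
5. Keep the unadjusted test as a supportive analysis.

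The cost is SAP wording and a few lines of code, with no new data or participants. The small downsides are the missing-covariate rule and a slightly more involved interval.

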7.4 Other prespecified and exploratory outcomes

7.4.1 Medication adherence

Proportions of patients considered adherent to lipid-lowering medication prescriptions (PDC \geq 80%) are compared between the Immediate Results and Delayed Results arm using either a Z-test of proportions or chi-squared test. In the event of small cell counts, we will employ Fisher's exact test to ensure the validity of the results. We will compute the relative risk and 95% confidence intervals to quantify the strength and direction of the association.

7.4.2 Cascade testing

The number of first-degree relatives undergoing genetic testing within 6 months will be recorded. Mean numbers and standard deviations of first-degree relatives tested will be calculated for each arm. A Poisson regression or negative binomial regression (in case of overdispersion) will be used to compare the rates of cascade testing between the two study arms. Potential confounders may be included in regression modeling to ensure the robustness of findings.

7.4.3 Self-reported quality of life

Mean change scores (6-month scores minus baseline scores) and standard deviations for both PCS and MCS of the VR-12 will be calculated for each arm. Independent samples t-tests will compare differences in mean change between the two arms for both PCS and MCS. Multivariable linear regression models (e.g. ANCOVA) may be fit to account for potential confounding variables.

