6.3.3. Self-reported quality of life

Self-reported quality of life is assessed via the baseline and end-of-study surveys, using the Veterans RAND 12-Item Health Survey (VR-12).¹⁰⁻¹² The VR-12 computes two continuous composite scores, a physical component summary (PCS) and a mental component summary (MCS).

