7.4.5 Categorical and ordinal outcome measures

The following measures are compared between treatment groups among the ITT populations using standard methods for categorical data analysis:^{27,28}

- Self-reported physical activity
- Self-reported smoking status
- Self-reported saturated fat consumption
- Self-reported patient activation (categorical score)
- Self-reported feelings about genomic testing results (Immediate Results arm only, items)
- Preferences for receiving genetic test results (Immediate Results arm only)

Frequency of end-of-study self-reported responses to study surveys, including categorical, ordinal, and Likert items, will be reported by treatment group (n, %). Binary logistic regression will be used to compare end-of-study dichotomous outcomes between treatment groups. To assess post-treatment ordered outcomes (e.g., lifestyle behaviors along the transtheoretical model continuum) between treatment arms, we will use ordinal logistic regression (e.g., cumulative logit model). Initial models will include treatment group assignment, and when available, baseline measures as covariates.

Treatment effect is characterized by an odds ratio estimate presented with standard error, 95% confidence interval, and *P* value.

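### VR-12 scores get change-score t-tests while PAM-13 and BMQ get baseline-adjusted ANCOVA: a small, avoidable loss of precision, not a bias

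*SAP*

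**What the plan says.** SAP section 6.3.3 describes the measure: "Self-reported quality of life is assessed via the baseline and end-of-study surveys", and "The VR-12 computes two continuous composite scores", PCS and MCS. Each participant should therefore have a baseline and a 6-month value on a continuous scale.

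Section 7.4.3 then sets the analysis in three sentences. The description comes first: "Mean change scores (6-month scores minus baseline scores) and standard deviations for both PCS and MCS of the VR-12 will be calculated for each arm". The comparison follows: "Independent samples t-tests will compare differences in mean change between the two arms for both PCS and MCS". Last comes an option: "Multivariable linear regression models (e.g. ANCOVA) may be fit to account for potential confounding variables". That sentence does not name the baseline score as the covariate, and it does not say which result leads if the two analyses differ.

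Section 7.4.6 covers the PAM-13 linear score and the BMQ, which are also collected on the baseline and end-of-study surveys (6.4.1, 6.4.2). Its wording is definite: "Analysis of covariance (ANCOVA) is used to compare continuous follow-up measures, including participant baseline measures, when available, and treatment group assignment". Section 7.4.5 does the same for the categorical and ordinal survey items: "Initial models will include treatment group assignment, and when available, baseline measures as covariates".

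The general rule in section 7.1 reads "No prespecified covariate adjustment is planned", which does not fit 7.4.5 or 7.4.6 as written.

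**The concern.** VR-12 is the only continuous survey outcome compared between arms whose main analysis does not condition on its own baseline score. The FACToR score is also listed in 7.4.6, but it is given to the Immediate Results arm only and allows no comparison between arms. The SAP gives no reason for treating VR-12 differently.

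Subtracting the baseline fixes its coefficient at 1. ANCOVA estimates that coefficient, which is normally below 1 for a questionnaire score. Two things follow from fixing it at 1. The interval for the arm difference is usually wider than the collected data require. Also, a chance difference between arms at baseline carries over, with opposite sign, into the estimated effect.

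The option in 7.4.3 does not settle this. It is permissive, and it gives confounding as the reason, which randomisation already deals with. The reason to adjust here is precision and protection against chance imbalance. At stake is the width of the interval on quality of life, and clarity about which VR-12 result is the main one.

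**Working it through.** **Inputs from the SAP.** Allocation is 1:1 (3.3). The target is 244 randomised, 122 per arm, allowing for up to 20% loss from 97 per arm (3.2). That step reproduces: 97/0.8 = 121.25, rounded up to 122 per arm, or 244 in total. The SAP gives no SD, effect size, power or baseline-to-follow-up correlation for VR-12, so it has no VR-12 figure to reproduce.

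**Assumptions.** The correlation rho is shown from 0.5 to 0.9. The slope on baseline is the same in both arms. For scale only, 97 per arm have both surveys.

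**General result.** Let s0 and s1 be the baseline and 6-month SDs. The variance of the arm difference is 2/n times:

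- change score: s0² + s1² − 2·rho·s0·s1
- ANCOVA: s1²·(1 − rho²)

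The first minus the second is s0² − 2·rho·s0·s1 + rho²·s1² = (s0 − rho·s1)². This is never negative, so ANCOVA is never less precise, apart from the one degree of freedom spent on the slope (194 − 3 = 191 instead of 194 − 2 = 192). The gain is zero when s0 = rho·s1. For example, with rho = 0.8, s0 = 1 and s1 = 1.25, the change-score variance is 1 + 1.5625 − 2 = 0.5625 and the ANCOVA variance is 1.5625 × 0.36 = 0.5625.

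**Equal SDs (s0 = s1).** The two variances become 2(1 − rho) and 1 − rho², with ratio (1 + rho)/2. The interval narrows by 1 − √ratio. The last column is the power of ANCOVA for an effect that the change-score test detects with 80% power.

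| rho (assumed) | Variance ratio, ANCOVA/change | 95% CI narrower by | ANCOVA power |
|---|---|---|---|
| 0.5 | 0.75 | 13.4% | 90% |
| 0.6 | 0.80 | 10.6% | 88% |
| 0.7 | 0.85 | 7.8% | 86% |
| 0.8 | 0.90 | 5.1% | 84% |
| 0.9 | 0.95 | 2.5% | 82% |

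**In score SDs.** At 97 per arm, the difference detectable with 80% power at two-sided 0.05 is (1.96 + 0.84) × √(2/97) × √v, where v is 2(1 − rho) or 1 − rho². Change score against ANCOVA gives 0.40 against 0.35 at rho 0.5, 0.31 against 0.29 at rho 0.7, and 0.180 against 0.175 at rho 0.9.

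**Chance imbalance.** With equal SDs, a baseline difference D between arms moves the change-score estimate by (1 − rho)·D in the opposite direction. One standard error of D is √(2/97) = 0.14 SD. The shift is then about 0.07 SD at rho 0.5 and 0.04 SD at rho 0.7. ANCOVA removes it.

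**Simulation check.** With equal SDs, 97 per arm, no true effect and 4,000 runs, the variance ratio was 0.76 at rho 0.5 and 0.86 at rho 0.7, against 0.75 and 0.85 from the formula. The mean estimates were close to zero for both methods (−0.006 and −0.004 at rho 0.5; −0.001 for each at rho 0.7).

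**The case against.** The strongest reply is that nothing here is wrong. A t-test on change scores is valid in a randomised trial. Section 7.4.6 applies to a closed list of measures that does not include VR-12, so 7.4.3 and 7.4.6 do not contradict each other. The VR-12 method also matches that of the primary LDL-C outcome, which is a t-test on change (5.1, 7.2). PAM-13 and BMQ sit in the exploratory group of section 6.4, while VR-12 is among the other prespecified outcomes of 6.3. Finally, sections 7.1 and 7.5 permit adjustment for precision, and baseline VR-12 will be reported by arm (4.5).

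Most of that stands. This is a choice between two valid estimators, and the contrast with 7.4.6 is an unexplained difference in method. The permissions do not remove the point, however. Section 7.5 makes added covariates supplemental, so the t-test remains the main VR-12 result. Agreement with the primary analysis is no reason to prefer the less efficient method here.

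Three stronger readings are tempting and are not supported:

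- **The change-score test loses precision whenever rho is below 1.** This holds only with equal SDs at both times; the worked case at rho 0.8 shows no loss.
- **The gain is worth 18% to 33% more participants.** That range comes from 1/0.85 and 1/0.75, so it assumes rho between 0.5 and 0.7. At rho 0.8 and 0.9 the equivalents are about 11% and 5%, and the SAP supports no particular value.
- **The trial could miss harm to quality of life.** The SAP gives VR-12 no safety role, and no decision depends on it.

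**Conclusion.** The point holds as a low-severity matter of precision and consistency. Section 7.4.3 leaves unused some of the information in a baseline score that it already requires, and it offers two analyses without ranking them beyond definite against optional wording.

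Under equal SDs and an assumed rho of 0.5 to 0.9, the ANCOVA variance is 0.75 to 0.95 times the change-score variance and the 95% interval is about 13% to 2.5% narrower. With unequal SDs the gain can be larger or smaller, down to nothing, but never negative apart from the one degree of freedom.

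A reader might infer that the planned VR-12 comparison is biased. It is not: both estimators are unbiased under randomisation. VR-12 falls among the analyses that section 5.4 treats as exploratory, so no confirmatory conclusion of the trial is affected.

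**What to change.** In section 7.4.3, state that 6-month PCS and 6-month MCS are each compared between arms by ANCOVA, with arm and the corresponding baseline score in the model, and that this is the main VR-12 analysis. Report the adjusted mean difference with its 95% confidence interval. Keep mean change and SD by arm as description. If the t-test on change is retained, label it supplementary. Drop confounding as the reason for the baseline term and give precision and chance imbalance instead.

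In section 7.1, say that the baseline value of the outcome is a prespecified covariate in 7.4.3, 7.4.5 and 7.4.6 where it is available, and that no other adjustment is prespecified. This also removes the mismatch between 7.1 and the two sections that already adjust.

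The cost is a short SAP amendment, best logged before outcomes are examined by arm, and one degree of freedom per model. No new data are needed: the change score already requires the baseline score, and randomisation follows completion of the baseline survey (4.3).
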